6.10. Health Outcomes/Quality-of-Life Analyses

The assessment of PROs, including disease-specific symptoms and health-related quality of life, will be assessed using the EORTC QLQ-30 and QLQ HCC-18.

The EORTC QLQ-C30 is a general measure of quality of life in cancer patients (Aaronson et al. 1993). It is a self-reported instrument consisting of 30 items covered by 1 of 3 dimensions: Global health status/quality of life (2 items); functional scales (15 total items addressing either physical, role, emotional, cognitive, or social functioning); symptom scales (13 total items addressing either fatigue, nausea/vomiting, pain, dyspnea, insomnia, appetite loss, constipation, diarrhea, or financial impact).

To assess disease-specific symptoms of HCC patients, the HCC-specific module (EORTC QLQ HCC-18) will be used. The EORTC QLQ HCC-18 is an 18-item HCC-specific supplemental module developed to augment QLQ-C30 and to enhance the sensitivity and specificity of HCC-related QOL issues (Blazeby et al. 2004).

Both the EORTC QLQ-30 and QLQ HCC-18 will be administered at baseline, at every cycle starting from Cycle 2, and at discontinuation (Visit 801).

Summary descriptive statistics will be provided for the PRO data (that is, EORTC QLQ-C30 and QLQ HCC-18) at each assessment. This summary will include mean, standard deviation, median, minimum, and maximum. Composite scores for each dimension and total scores will be evaluated in aggregate (that is, median values for each study arm at a given time point) and average change from baseline will be reported for each arm at each time point. Time to symptomatic progression may also be evaluated, and longitudinal analyses, such as repeated measures, may be performed. Other exploratory longitudinal analyses may be performed.

6.11. Bioanalytical and Pharmacokinetic/Pharmacodynamic Methods

Pharmacokinetic and PK/pharmacodynamic analyses are the responsibility of the PK scientist. The following sections are for information only. Detailed plans will be in the PK/pharmacodynamic analysis plan.

6.11.1. Pharmacokinetic Methods

The plasma-concentration-versus-time data together with information on dosing and patient characteristics will be pooled and analyzed using a population PK analysis approach. Nonlinear mixed-effect modeling (NONMEM) will be used for the estimation of the population PK parameters of LY2157299. Sorafenib PK will be assessed against a published sorafenib population PK model.

All patients who have completed at least 2 days of sampling will be included in the PK analysis. LY2157299 PK will be modeled using NONMEM. These population parameters will describe the average dose-concentration relationship in the target population, the influence of fixed effects (such as weight or age) on a PK parameter of interest, the interindividual variation in the PK parameter, and the residual variation in the observed concentration.

For the purposes of the JBAS CSR, plasma-concentration data will be illustrated graphically and summarized descriptively. If data is sufficient, then data from patients in this study will be modeled using the population approach for characterizing LY2157299 PK.

Exploratory PK/pharmacodynamic analyses will be conducted to identify the exposure-response (biomarker) relationship in this study. The PK and PK/pharmacodynamic analyses may be reported as separate stand-alone reports for this study. Additional analyses such as exposure-response using TTP and/or other appropriate clinical endpoints may be explored, if data warrant.

The version of any software used for the analysis will be documented, and the program will meet Lilly requirements for software validation. It is possible that other validated equivalent PK software programs may be used if appropriate, warranted, and approved by global PK management.

6.11.2. Pharmacodynamic Methods

Pharmacodynamic parameters (for example, E-cadherin, pSMAD, TGF- β 1, AFP) will be analyzed using pharmacodynamic data from all patients who underwent PD assessments. The association between changes in PD parameters and clinical endpoints will be explored to determine their value as predictive biomarkers of drug effect on overall survival. These analyses will include creating and using two indicator variables to sub-group patients who have at least a 20% reduction from baseline in AFP and TGF- β 1 levels respectively. Exploratory analyses to identify optimal cutoff points for these two variables may be carried out. The relative day of when 20% reduction (if occurs) in each of these biomarkers for each patient will be derived and summary statistics of the distribution provided, in order to understand when it is likely when a pharmacodynamic effect might occur to aid further development.

Additional exploratory analyses may be carried out dependent upon results from other studies using LY2157299.

Details of all these analyses will be provided in the Table, Figure, Listing (TFL) shells.

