The scientific justification of investigating LY2157299 in HCC is compelling based on the role of TGF- $\beta$  in the process of fibrosis and cirrhosis leading to HCC. The evidence of antitumor effects in several preclinical models with TGF- $\beta$ -dependent tumor growth and their inhibition by other TGF- $\beta$  inhibitors, such as LY2109761 and LY364947, suggest that LY2157299 will have activity in HCC. Preclinical data of the combination of LY2157299 and sorafenib shows the potentiation of sorafenib activity in vitro and ex vivo study and implies the possibility that this combination may be more effective than sorafenib alone. In addition, clinical data from HCC patients who have progressed on sorafenib and were treated with LY2157299 had antitumor activity (Study H9H-MC-JBAK [JBAK]). Based on recent interim analysis including 106 patients from Study JBAK, which studied LY2157299 in HCC, treatment resulted in a median time-to-tumor progression (TTP) of 12 weeks (18.3 weeks in patient without previous sorafenib treatment) and alpha fetoprotein (AFP) responses (as defined by >20% reduction from baseline) in 22% of patients.

The present Phase 2 study will further explore the safety and efficacy of LY2157299 alone or in combination with sorafenib in Asian patients with HCC who have not received prior systemic treatment for advanced disease.

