#### **5.1.5.1. Brief Summary of Patients Treated in Study JBAK (LY2157299 Monotherapy in Patients with Advanced Hepatocellular Carcinoma Who Failed or Were Not Eligible to Receive Sorafenib)**

In Study JBAK, patients with advanced HCC who progressed on sorafenib or were ineligible to receive sorafenib; patients were eligible if they had advanced Child-Pugh A/B7 HCC, Eastern Cooperative Oncology Group (ECOG) PS  $\leq$ 1, measurable disease (Response Evaluation Criteria in Solid Tumors [RECIST] version 1.1), and  $\leq$ 1 prior systemic regimen. LY2157299 was

administered as intermittent dosing of 14 days on/14 days off (28 days = 1 cycle). Patients were randomized to either 160 mg/day (Arm A) or 300 mg/day (Arm B) LY2157299.

An interim analysis for Study JBAK was conducted after enrollment of 106 patients with elevated AFP levels (AFP  $\geq$ 1.5 times the upper limit of normal [ULN]).

One hundred six patients were enrolled (Arm A=37; Arm B=69) and included 92% non-Asians. Baseline characteristics (Arm A/B) were a median age of 61/66 years; PS of 0, 60%/51%; Child-Pugh A, 97%/86%; and etiology: hepatitis C (30%/33%), hepatitis B (24%/25%), and alcohol (22%/22%). Overall, 78%/83% of patients had received prior sorafenib; 64%/58% of patients had AFP levels  $\geq$ 400 ng/mL. Median TTP was 12.0 weeks (90% CI: 7.1, 12.6) in the overall population (Arm A, 12.6 weeks; Arm B, 10.9 weeks). In 20 sorafenib-naïve patients, TTP was 18.3 weeks (90% CI: 6.3, nonestimable). Disease control rate was 34.9%. In sorafenib-naïve patients, disease control rate was 45%. AFP decline of  $>$ 25% occurred in 21/106 patients (20%). Four patients discontinued treatment due to a drug-related TEAE. The most common Grade 3/4 related TEAEs in patients were neutropenia (n=3), GI bleeding (n=2), fatigue (n=2), and anemia (n=2) (Faivre et al. 2013).

Of the information collected to monitor the potential for cardiac toxicity during treatment (ECG, echocardiograph, troponin I, and BNP), none were considered of clinical significance.

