5.3. Method of Assignment to Treatment

For this study, approximately 120 patients with advanced HCC who have not received prior systemic treatment and who meet all criteria for enrolment will be randomly assigned by the interactive web-response system (IWRS) to receive LY2157299 monotherapy, LY2157299 plus sorafenib, or sorafenib plus LY2157299-matched placebo in a 1:2:1 ratio after completing the screening at Visit 0. Additionally, patients who receive sorafenib and investigators will be blinded to the LY2157299 or placebo assignment for those arms (Arms 2 and 3).

A dynamic allocation method, introduced by Pocock and Simon (1975) (and extended for unequal treatment group sizes by Han et al. [2009]), will be adopted to minimize imbalance between treatment arms according to the following factors:

- AFP (>200 ng/mL vs ≤200 ng/mL)
- portal vein thrombosis (yes vs no)

The randomization parameter P will be set at 0.9 to maximize the benefit of the allocation procedure while keeping treatment assignments unpredictable. Randomization will be monitored periodically, and the randomization parameter will be modified if necessary.

Assignment to treatment groups will be determined by a computer-generated random sequence using an IWRS.

The IWRS will be used to assign blister packs containing study drug to each patient. Site personnel will confirm that they have located the correct blister packs by entering a confirmation number found on the blister packs into the IWRS.

6. A Priori Statistical Methods

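### SAP 6.11.2 specifies only 20% yes/no indicators, plus an optional uncorrected cut search, for relating AFP and TGF-β1 change to OS; it names no continuous model and no AFP baseline floor

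*SAP*

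**What the plan says.** SAP 6.11.2 sets the aim: "The association between changes in PD parameters and clinical endpoints will be explored to determine their value as predictive biomarkers of drug effect on overall" (OS is the endpoint named). It then commits to one form of analysis: "These analyses will include creating and using two indicator variables to sub-group patients who have at least a 20% reduction from baseline in AFP", with a matching indicator for TGF-β1. It adds an option: "Exploratory analyses to identify optimal cutoff points for these two variables may be carried out". The analysis set is everyone with PD data, whatever their baseline level. The section gives no model for the continuous change, no baseline adjustment, no treatment interaction, no assessment visit for the indicator and no correction for a searched cut. Protocol 12.2.9 adds no model.

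Two statements limit how binding this is. SAP 6.11 introduces its subsections with "The following sections are for information only. Detailed plans will be in the PK/pharmacodynamic analysis plan", and SAP 6.11.2 leaves further detail to the table, figure and listing (TFL) shells.

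On the source of the 20% threshold, the Protocol's Study Rationale reports from JBAK "alpha fetoprotein (AFP) responses (as defined by >20% reduction from baseline) in 22% of patients". Protocol 5.1.5.1 describes the population: "An interim analysis for Study JBAK was conducted after enrollment of 106 patients with elevated AFP levels", meaning at least 1.5 times the upper limit of normal (ULN). In the present trial no criterion in Protocol 7.1 or 7.2 concerns AFP. AFP enters only as a balancing factor split at 200 ng/mL (SAP 5.3).

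**The concern.** AFP and TGF-β1 are continuous and measured repeatedly. A yes/no split treats a 21% fall and a 90% fall alike, and separates a 19% fall from a 21% fall. If that split is what relates the markers to OS, a useful marker can be missed. Choosing the cut from the same data without correction creates the opposite risk, an apparent cut-off with nothing behind it.

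For AFP there is a further problem. JBAK's rate describes patients with clearly raised AFP. Here a patient going from 5 to 4 ng/mL has fallen by exactly 20% and counts as a responder, though the change may be only measurement and biological noise. Such patients dilute any real signal.

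At stake is the reading of these markers for later development, not the trial's primary conclusion.

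**Working it through.** **Figures in the documents.** SAP 6.11.2 gives no power or precision figure. Two nearby figures check out.
- Protocol 5.1.5.1 reports an AFP fall of more than 25% in 21 of 106 patients: 21/106 = 19.8%, printed as 20%.
- SAP 5.2 gives 73% log-rank power. The formula is Φ(√(d × 1/3 × 2/3) × |ln 0.667| − 1.080), with d the deaths in the two compared arms and 1.080 the one-sided 14% point. With d = 75 (100 × 90/120) it gives 71.7%. With the 78.7 to 80.0 deaths implied by 0.0216/week, the stated accrual and 104 weeks, it gives 73.0% to 73.5%.

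**Inputs for the check.** 120 patients and 100 deaths (SAP 5.2); responder share 22% (Study Rationale, AFP in JBAK). Assumed: normal log ratio, log-linear effect on the hazard, two-sided 5% test. The SAP sets no test for this analysis; 5% is only a yardstick.

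**Step 1. Information kept by the split.** Relative efficiency = φ(z)² / [p(1 − p)], where z is the normal quantile at responder share p.
- p = 0.22: z = −0.772, φ(z) = 0.2961, so 0.0877 / 0.1716 = 0.511. Loss 49%.
- p = 0.50: 0.1592 / 0.25 = 0.637. Loss 36%.
- p = 0.10: 0.0308 / 0.09 = 0.342. Loss 66%.

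The formula holds for small effects. In simulations with responders at lower hazard, 55% to 57% was lost at p = 0.22.

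**Step 2. Power.** Simulated Cox score tests, follow-up ending at the 100th death, with the 22% of patients who have the largest falls at lower hazard:

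| HR per SD | Continuous | Split 22/78 |
|---|---|---|
| 1.28 | about 66% | about 36% |
| 1.32 | about 78% | about 44% |
| 1.42 | about 93% | about 62% |

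Repeat runs differ by one or two points. Direction matters: if the 22% were the higher-hazard group, split power would be about 46%, 54% and 73%. That is not the case of interest, in which an AFP fall goes with longer survival.

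**Step 3. Cut search.** With no association, taking the best of 17 cuts from the 10th to the 90th percentile in steps of 5 gives p<0.05 in about 30% of trials instead of 5%.

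**Step 4. Falls from noise alone.** For two log-normal measurements with no true change, P(fall ≥20%) = Φ(ln 0.8 / (s√2)), with s² = ln(1 + CV²). The documents give no within-patient CV, so a range is assumed:
- CV 5%: 0.1%
- CV 10%: 6%
- CV 15%: 15%
- CV 20%: 21%

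These are for one visit. If a fall at any of four visits counted, the chances would be 0.3%, 16%, 35% and 46%.

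**The case against.** A reader might infer that the SAP replaces continuous change with the indicators and so throws away half the information on both markers. The text does not support that. It plans to explore changes in PD parameters and says the indicators are among the analyses included. The Protocol synopsis also speaks of estimating biomarker changes, and SAP 6.1 provides for transformations. SAP 6.11 calls the subsections informational and points to a PK/PD analysis plan that is not among the documents. That plan may contain a continuous model, a baseline rule or a correction. This objection stands: what can be shown is that SAP 6.11.2 specifies only the indicators.

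The work is also exploratory, with no stated test or decision rule, and the cut search is optional. That stands too, so the power and error rates show scale and are not failures of a planned test. That a false marker would be carried into Phase 3 is possible but not shown.

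The 22% may not transfer. JBAK's interim set was monotherapy, 92% non-Asian, mostly sorafenib-pretreated and selected for raised AFP. No TGF-β1 rate is given. Hence the range over responder shares. A threshold-shaped effect would lose less.

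Finally, the 20% cut has a use: it matches JBAK's definition, and SAP 6.11.2 also derives the day it is reached. That supports keeping it as a description, but not as the only specified link to OS.

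**Conclusion.** The point holds as a gap in specification with a better method available at little cost. For a stated aim of judging predictive value for OS, SAP 6.11.2 names only 20% indicators and an uncorrected cut search, and sets no AFP floor.

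If the indicator carries the analysis, about 49% of the information is lost for AFP at JBAK's rate, or 36% to 66% for responder shares from 50% down to 10%. The cost in power is about 30 to 34 points at the effects examined. This rests on normality, log-linearity and a full 100 deaths. For TGF-β1 the documents give no responder share, so only the range applies. The noise concern is sound in principle, but its size runs from negligible to about one patient in five depending on an unknown CV. The share of patients here with normal AFP is also unknown.

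The primary OS conclusion is not touched.

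**What to change.** In SAP 6.11.2, and carried into the PK/PD analysis plan and TFL shells:
- Make the main biomarker-OS analysis a proportional hazards model on the continuous log ratio to baseline at one fixed, pre-stated landmark visit, with OS counted from that landmark. Adjust for log baseline and include a treatment interaction, since predictive value for drug effect cannot be judged without one.
- Keep the 20% indicator as a description for comparison with JBAK. For AFP, compute it only in patients with baseline AFP at least 1.5 times ULN, and repeat the continuous AFP model with that restriction as a sensitivity analysis.
- Report any searched cut with a maximally-selected-statistic or permutation p-value.
- When citing JBAK's AFP rate, state the cut it refers to, because the Protocol gives rates for both 20% and 25%.

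The cost is wording, one extra model per marker, and a slope slightly harder to read than responder versus non-responder. Patients who die or have no sample before the landmark drop out of the model, so an early visit loses fewer. No new data are needed.

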Cycle (Visit)	Baseline (Visit 0)			Patient on Study Treatment									Post Discontinuation Follow-Up Periods		Comments	
				Cycle 1 (Visit 1)			Cycle 2 (Visit 2)			Cycle 3, n a (Visit 3, etc)			30-Day Safety Follow-Up (v801)	Long-Term Follow-Up b (v802, v803, etc)		
Relative Day Within a Cycle	≤28	≤14	≤7	1 c,d	8 c	14 c	15	22	1 c	14 c,e	22	1 c			14 c,e	
DW-MRI and then DCE-MRI (performed sequentially in the visit)			X								X				Baseline scan to be performed within 10 days prior to first study drug dose.  The second scan will be performed at Cycle 2 Day 22 ± 3 days.  eGFR should be ≥30 mL/min/1.73 m  to allow safe use of GBCA, The creatinine needed to calculate the eGFR may be obtained from the serum chemistries at baseline for the first MRI and at Cycle 2 Day 14 for the second MRI at Cycle 2 Day 22.	
Laboratory tests														Refer to Attachment 2		
Pregnancy test			X													
ECG chemistry		X							X			X		Xi	Xi	Cycle 2, 3, 4, and every other cycle (Cycle 6, Cycle 8, etc)

Cycle (Visit)	Baseline (Visit 0)			Patient on Study Treatment									Post Discontinuation Follow-Up Periods		Comments	
				Cycle 1 (Visit 1)				Cycle 2 (Visit 2)			Cycle 3, n a (Visit 3, etc)		30-Day Safety Follow-Up (v801)	Long-Term Follow-Up b (v802, v803, etc)		
Relative Day Within a Cycle	≤28	≤14	≤7	1 c,d	8 c	14 c	15	22	1 i,c	14 c,e	22	1 c			14 c,e	
Special chemistry			X		X	X		X	X	X	X	X	X	X		Includes troponin and BNP
Hematology			X		X	X		X	X	X	X	X	X	X		
Serum chemistry			X		X	X		X	X	X	X	X	X	X		
Urinalysis		X							X			X		X		
Hepatitis B and C serology	X l								X m			X m		X m		
Urine C-terminal telopeptides of Type 1 collagen		X							X			X				
PK sampling				X		X	X	X	X			X				See Attachment 5 for timing of samples
Serum markers		X		X		X			X	X		X	X	X		AFP, AFP L3, E-cadherin, PIVKA II
Immunophenotype				X					X			X		X		
TGF-β + PF4				X		X			X	X		X	X	X		
MAP				X		X				X			X	X		

Cycle (Visit)	Baseline (Visit 0)			Patient on Study Treatment									Post Discontinuation Follow-Up Periods		Comments
				Cycle 1 (Visit 1)			Cycle 2 (Visit 2)			Cycle 3, n a (Visit 3, etc)			30-Day Safety Follow-Up (v801)	Long Term Follow-Up b (v802, v803, etc)	

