Abbreviations: AFP = alpha-fetoprotein; aPTT = activated partial prothrombin time; BCLC = Barcelona Clinic Liver Cancer; BNP = brain natriuretic peptide; BSC = best supportive care; C = cycle; CLIP = Cancer of the Liver Italian Program; CT = computed tomography; CTCAE = Common Terminology Criteria for Adverse Events; DCE-MRI = dynamic contrast-enhanced magnetic resonance imaging; DW-MRI = diffusion-weighted magnetic resonance imaging; ECG = electrocardiogram; ECOG = Eastern Cooperative Oncology Group; eGFR = estimated glomerular filtration rate; EORTC = European Organisation for Research and Treatment of Cancer; exam = examination; GBCA = gadolinium-based contrast agent; HBsAg = hepatitis B surface antigen; HCC = hepatocellular carcinoma; INR = international normalized ratio; MAP = multi-analyte panel; mRECIST = modified Response Evaluation Criteria in Solid Tumors; MRI = magnetic resonance imaging; PF4 = platelet factor 4; PGx = pharmacogenomics; PIVKA II = prothrombin induced by vitamin K absence; PK = pharmacokinetic; PT = prothrombin time; QLQ = quality-of-life questionnaire; RNA = ribonucleic acid; TGF- $\beta$  = transforming growth factor beta.

- a Patients on study for more than 1 year (before entering extension period) only need tests to be performed on Day 1 of each cycle.
- b Follow-up consists of Visit 802 and all subsequent visits (60 days  $\pm$  7 days).
- c To be performed predose LY2157299 or sorafenib
- d A delay at the start of a cycle (Day 1) of no more than 3 days because of holidays, weekends, inclement weather, or other justifiable events will be permitted and not counted as a protocol violation.
- e In extenuating circumstances, the “on study drug” window for LY2157299 is allowable from Day 10 to Day 14.
- f Child-Pugh, BCLC, and CLIP assessment procedures can be found in [Attachment 6](#), [Attachment 7](#), and [Attachment 8](#), respectively.
- g If drug-related toxicity is present 30 days after the last cycle of study drug, patients must be followed up approximately every 30 days until toxicity resolution, stabilization, another therapy is initiated, or death.
- h Echocardiography with Doppler can be performed up to 3 days prior to Day 1.

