6.9. Efficacy Analyses

The following are definitions of the primary and secondary efficacy endpoints:

Primary Endpoint:

- **Overall Survival (OS) duration** is measured from the date of randomization to the date of death from any cause. For each patient who is not known to have died as of the data-

inclusion cut-off date for a particular analysis, OS will be censored for that analysis at the date of last contact prior to the data inclusion cutoff date (contacts considered in the determination of last contact date AE date, lesion assessment date, visit date, and last known alive date).

Secondary Endpoints:

- **Time to Progression (TTP) duration** is measured from the date of randomization to the first date of objective progression of disease based on Response Evaluation Criteria in Solid Tumors (RECIST) version 1.1 prior to the start of any post-discontinuation anti-cancer therapy. For each patient who is not known to have had a progression of disease as of the data-inclusion cut-off date, date of death, or date of initiating any post-discontinuation therapy, time to progression will be censored for that analysis at the date of the patient's last tumor assessment prior to that date.
- **Time to Progression rate at 3 months, 6 months, 9 months, 12 months** is defined as the proportion of patients not having objective progression (based on RECIST version 1.1) at 3, 6, 9, and 12 months respectively after the time from date of randomization estimated from the TTP distribution.
- **Progression-Free Survival (PFS) duration** is measured from the date of randomization to the date of first observation of objective progression (based on RECIST version 1.1) or death from any cause, prior to the start of any post-discontinuation anti-cancer therapy, whichever occurs first. For patients who are not known to have died or progressed as of the data-inclusion cut-off date or as of the date of post-discontinuation anti-cancer therapy, PFS time will be censored at the date of the last tumor assessment prior to that date.
- **Progression-Free Survival rate at 3 months, 6 months, 9 months, 12 months** is defined as the proportion of patients not having objective progression (based on RECIST version 1.1) or death at 3, 6, 9, 12 months respectively after the time from date of randomization estimated from the PFS distribution.

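### SAP 6.11.2 relates an undated 20% fall in AFP or TGF-beta1 to OS counted from randomisation; if a fall at any sample counts, guarantee time favours responders in this exploratory analysis

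*SAP*

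**What the plan says.** SAP 6.11.2 will relate changes in pharmacodynamic markers to outcome, to "determine their value as predictive biomarkers of drug effect on overall survival". The method is stated as "creating and using two indicator variables to sub-group patients who have at least a 20% reduction from baseline in AFP" and, separately, in TGF-beta1. A search for better cutoffs may follow. The section adds: "The relative day of when 20% reduction (if occurs) in each of these biomarkers for each patient will be derived and summary statistics" of its distribution will be given, so as to learn when an effect tends to appear. No visit, window, landmark or time-dependent rule is stated, and nothing is said about patients who have a baseline value only. Protocol 12.2.9 is equally silent.

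OS "is measured from the date of randomization to the date of death from any cause" (SAP 6.9). In the Study Schedule (Protocol Attachment 1), the serum markers row ("AFP, AFP L3, E-cadherin, PIVKA II") is marked at baseline, on Day 1 and Day 14 of each cycle, and at Visit 801. The TGF-beta row is marked at the same on-treatment visits and at Visit 801. After one year, patients "only need tests to be performed on Day 1 of each cycle".

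SAP 6.11 describes its subsections as informational and says: "Detailed plans will be in the PK/pharmacodynamic analysis plan". SAP 6.11.2 ends: "Details of all these analyses will be provided in the Table, Figure, Listing (TFL) shells". Neither document was supplied.

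**The concern.** The classifier uses information that arises after the survival clock has started. If a fall at any sample counts, a patient whose marker first falls at week 20 must have lived, and normally stayed on treatment, for 20 weeks. Those weeks are credited to the responder group. Patients who die or stop early have few samples and tend to be classed as non-responders. Responders then show longer OS even if the marker says nothing about survival.

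The any-sample reading is not stated, but it is the natural one. If a single fixed visit defined response, the day of the fall would be nearly constant and its distribution would tell the reader nothing.

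At stake is a biomarker signal intended to help further development. The optional cutoff search would inherit the same bias. The primary Bayesian OS comparison does not use these indicators.

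**Working it through.** The documents give no effect size or power for this analysis, so there is no stated figure to reproduce. The check asks what a yes/no indicator returns when the marker has no effect (true hazard ratio 1).

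**Inputs from the documents.** Death hazard 0.0216/week (SAP Table JBAS.5.1). It reproduces with 4-week months: ln2/(6.5×4) = 0.02666, ln2/(8.8×4) = 0.0197, and (150×0.02666 + 410×0.0197)/560 = 0.0216. N = 120. The AFP response rate of 22% comes from Study JBAK (Protocol Synopsis and 5.2), whose interim population was 92% non-Asian and mostly sorafenib-pretreated (Protocol 5.1.5.1). No TGF-beta1 rate is given.

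**Assumptions.** Samples at weeks 2, 4, ... 52, then every 4 weeks, while alive and on treatment. Response at each sample is independent of survival, calibrated so that 22% of sampled patients respond. OS is censored at 104 weeks.
- (A) Stopping unrelated to death: death 0.0216/week throughout; discontinuation 0.03, 0.05 or 0.10/week.
- (B) Stopping predicts death: death 0.010 or 0.0144/week on treatment and 0.03 or 0.04/week after; discontinuation 0.03 or 0.057/week.

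**Mechanism.** The chance of being alive and on treatment at week t is exp(−(death + discontinuation)×t). With 0.0216 + 0.05 = 0.0716/week:
- week 2: exp(−0.1432) = 0.87
- week 8: exp(−0.5728) = 0.56
- week 26: exp(−1.8616) = 0.16

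A fall first showing at week 26 can be seen in about one patient in six, each with 26 weeks of survival already assured.

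**Results, responder versus non-responder, true hazard ratio 1.**

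| Falls counted | Hazard ratio |
|---|---|
| Week 2 only, unsampled patients excluded | about 1.00 |
| Week 2 only, unsampled counted as non-responders | 0.92-0.95 |
| Up to week 8 | 0.90-0.95 |
| Up to week 26 | 0.74-0.86 |
| No limit | 0.57-0.84 (A 0.68-0.84, B 0.57-0.71) |
| Week-6 landmark, alive and on treatment | 0.98-1.02 |

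In trials of 120 patients, a one-sided 2.5% test falsely favoured responders in 1.8-2.6% (week 2), 2.9-5.0% (week 8), 6-23% (week 26) and 7-66% (no limit).

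**Sensitivity.**
- *Visit 801.* A sample about 4.3 weeks after stopping barely moves the hazard ratios. Without it the share with no post-baseline sample runs from 1 − exp(−2×0.04) = 8% to 1 − exp(−2×0.1216) = 22%; with it, 3-5%.
- *Time on treatment set to median TTP in Study JBAK.* With no limit on timing, 12 weeks gives 0.75 (23% responding) and 18.3 weeks gives 0.68 (28% responding).
- *Fall as a time-dependent Cox covariate.* A gives 0.99-1.01. B gives 0.94-0.97 (week 8), 0.86-0.93 (week 26) and 0.81-0.91 (no limit): the bias shrinks but does not vanish.

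**The case against.** The strongest reply is that this is silence in a summary, not a wrong method. SAP 6.11 defers to a PK/PD plan and 6.11.2 to TFL shells; either may fix the window, and a week 2 definition would carry almost no bias. That stands, and it limits the point. It does not remove it, because the SAP itself sets the threshold and the endpoint, and the missing timing rule decides whether the null hazard ratio is near 1.0 or near 0.7.

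The size is also open to attack, fairly. Response timing, discontinuation and off-treatment hazard are all assumed. Discontinuation at 0.10/week implies a median of ln2/0.10 = 6.9 weeks, short against the 18.3-week median TTP in sorafenib-naive JBAK patients. Scenario B is supported only in part: Protocol 7.3.1 lists progression as a reason to stop, yet puts the decision on clinical symptoms, and Protocol 10.1 lets patients continue despite objective progression. Nor does sampling end entirely with treatment, since Visit 801 follows.

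A further reply is that the SAP wants to learn when the fall occurs, so fixing week 6 presumes the answer. The day of the fall can still be summarised in full; the landmark governs only the link to OS.

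A reader might infer more: that the SAP commits to a biased analysis, that no safeguard exists, or that a spurious hazard ratio near 0.6 is to be expected. The documents support none of these. The any-sample rule is implied rather than stated, two governing documents are unseen, and the lowest values need late falls together with stopping that predicts death.

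**Conclusion.** The concern holds as a minor point. SAP 6.11.2 gives a post-baseline classifier with no timing rule and an endpoint counted from randomisation; on its natural reading, guarantee time favours responders. The direction was the same in every setting that let falls beyond week 2 count. With 22% responding, the size runs from slight (0.90-0.95) if falls come by week 8 to large (0.57-0.84) if they may come at any time, and it depends on hazards, discontinuation and response timing that the documents do not give. A week 2 definition is close to unbiased only if patients with no post-baseline sample are left out. The analysis is exploratory and carries no decision rule, and the primary Bayesian OS conclusion is unaffected. If the PK/PD plan or TFL shells already hold a suitable rule, a cross-reference closes the point.

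**What to change.** In SAP 6.11.2, carried into the PK/PD plan and TFL shells:
- Define response by a fixed early window, for example a 20% fall at any sample up to Cycle 2 Day 14 (day 28 + 14 = 42, week 6).
- Count OS from that landmark among patients alive, on treatment and sampled by then.
- Exclude patients with no post-baseline sample, and report how many there are.
- Use the same landmark for any cutoff search.
- As support, fit a Cox model with the fall as a time-dependent covariate, using the day already derived. Re-base that day to randomisation, because SAP Table JBAS.6.1 counts study day from first dose. Note that some bias can remain, since regular sampling ends with treatment (apart from Visit 801) and stopping may predict death.

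No new data are needed. The cost is precision and scope. Under the assumed rates the landmark keeps between 120×exp(−6×0.1216) = 58 and 120×exp(−6×0.04) = 94 patients, a loss of roughly 20-50%. Later responders count as non-responders: of 21-24 any-time responders, 13-18 remain if falls come by week 8, but only 6-9 with no limit, so power is low if falls are late. The result applies only to patients still on treatment at the landmark.
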